7.2.3 SAE declaration

All defined **Serious Adverse Events (SAEs)** occurred **after the informed consent up to 30 days after the last study drug administration**, whether or not ascribed to the study, will be recorded in the Serious Adverse Event pages. After this delay only fatal SAE and SAE related to the IMP must be recorded.

Serious Adverse Event (serious or not) will not be recorded after the start of a new out-of-study treatment or after disease progression (fatal event excluded)

All Serious Adverse Events must also be reported on the Adverse Event page of the CRF.

In a case of Serious Adverse event The Investigator must immediately:

- **SEND, by fax, the SAE pages to**

**SAFETY DESK:
[contact]**

All SAE forms must be dated and signed by the responsible Investigator or one of his/her authorized staff Members.

- Attach the photocopy of all examinations carried out and the dates on which these examinations were performed. Care should be taken to ensure that the patient's identity is protected and the patient's identifiers in the Clinical study are properly mentioned on any copy of source document. For laboratory results, include the laboratory normal ranges.
- Follow up of any Serious Adverse Event that is fatal or life threatening should be provided within one calendar week.

For serious adverse events, the following must be assessed: relationship to test substance, action taken, and outcome to date. The relatedness with concomitant treatment must also be evaluated. The Causality is initially assessed by the investigator. For serious adverse events, causality can be one of two possibilities:

- **Unrelated**
- **Related**

7.2.4 Follow up of Adverse Events and Serious Adverse events

- Any SAEs should be monitored until they are resolved or are clearly determined to be due to a patient's stable or chronic condition or underlying condition. Any additional information known after the event has been initially reported should be sent to the SAFETY DESK as soon as information becomes available.
- All adverse events must be documented and the outcome must be followed up until the return to normal or consolidation of the patient's condition.

7.3 Sponsor's responsibilities

During the course of the study, the Sponsor will report in an expedited manner all SAEs that are both unexpected and at least reasonably related to study drug, to the Health Authorities in each country in accordance with the law of March 5, 2012 international and local regulations, Ethics Committees, Clinical Trial Eudravigilance database and to the Investigators.

The expectedness of an adverse reaction will be determined by the Sponsor according to the Summary Product Characteristics of PROTOPIC 0,1%®.

The sponsor will report all safety information from the trial in the Annual Safety Reports and will notify the reports to the Health Authorities and Ethics Committees in accordance with international and local regulations.

7.4 Specific management of complications

7.4.1 Nosebleeds

Patients will have access to the standard management techniques for nosebleeds in HHT. ENT monitoring will be ensured before the start of administration, after 6 weeks of treatment and 6 weeks after the end of the treatment so as to note any modification to the nasal mucosa during the treatment (Appendix 3: ENT monitoring examination). The modalities for the management of nosebleeds will be given to the patients, as described in the "PNDS" (Protocole National de Diagnostic et de Soin), so that they may inform any doctor of the treatment modalities for the nosebleeds specific to this

pathology. Emergency document (see Appendix 4), accessible on the internet http://www.favamulti.fr/wp-content/uploads/2016/05/37_RO-Epistaxis.pdf, is given to the patients.

7.4.2 Perforation of the nasal septum

ENT monitoring will take place at each visit so as to note any modification to the nasal mucosa. Should there be any perforation of the nasal septum, the ENT monitoring will be prolonged until the perforation closes, as it generally does spontaneously.

7.4.3 Other complications associated with adverse events linked to topical tacrolimus

Common complications linked to topical administration described in the Summary of Product Characteristics are burning skin, pruritus, skin erythema, skin tingling, folliculitis, acne, herpes simplex, hyperesthesia (increased skin sensitivity, especially to hot and cold) and alcohol intolerance (facial flushing or skin irritation after consumption of an alcoholic beverage).

In case of the onset of a severe reaction, patients should stop product administration immediately. They must inform the investigator of the study as soon as possible and, if necessary, consult a doctor.

Adapted management of the complication will be administered.

7.4.4 Tacrolimus systemic absorption

Tacrolimus systemic absorption will be monitored in this study. FK506 dosages in blood are scheduled at Day 8, 22 and 43. Analysis will be centralized in "Hospices Civils de Lyon".

After transplantation, the optimal trough blood concentrations are generally between 5.0 and 15.0 ng/mL⁶⁴ and should be maintained below 20 ng/mL.

In the present study, no systemic absorption and effect are expected. However in case of positive dosage, from 5 ng/mL and above, the laboratory will immediately inform the investigator who will ask the patient to stop treatment.

In case of dosage higher than 20 ng/mL, the laboratory will immediately inform the investigator who will ask the patient to stop treatment and the patient will be hospitalized.

Any sign of infection due to immunosuppressive action should be reported immediately to the sponsor as SAE.

8 Data management

8.1 Electronic case report forms

All the information required by the protocol must be provided on the eCRF and an explanation is given for any missing data. All clinical or paraclinical data have to be transferred to the electronic case report forms as soon as they are obtained. The form

at the end of each visit must be dated and signed by the investigator thus indicating his or her approval of the data in the case report forms.

The database (items defined on the basis of the electronic case report forms) will be put together in collaboration with the Clinical Research Unit at the Pole IMER (Dr [name]).

8.2 Source documents

The source documents are the original documents, the data and dossiers from which the data concerning the patients will be reported in an electronic case report forms (Clinsight). These data include, amongst other things, the results of examinations, monitoring of the patient at the hospital and/or medical notes, self-monitoring forms, dispensation notes and medical correspondence.

The investigator must undertake to authorize direct access to the source data for the study during control visits, audits or inspections.

8.3 Archiving

The following documents concerning this research will be archived in the appropriate premises and locked in accordance with Good Clinical Practices for a period of 15 years following the end of the research by those responsible for the study:

- the original version of the consent forms signed by the participants,
- the protocol and its appendices and any amendments made to the protocol,
- electronic case report forms,
- all the other documents and letters concerning the research.

8.4 Electronic data management

The Clinical Research Unit at the Pole IMER will develop an electronic Case Report Form to collect data for the study.

The study data will be computerized in conformity with the law concerning electronic data, files and civil liberties (law 78-17 of January 6, 1978 modified by law 2004-801 of August 6, 2004). Data access will be restricted.

Electronic report forms will be available for each participating center. Electronic case report forms will be filled in via internet by the investigator. A user guide and online training will be available to investigators.

The investigator is responsible for the accuracy, quality and relevance of all data captured. As such, any changes in value must be validated in the eCRF. Data changes will be drawn in an audit trail.

Patients' eCRF will be printed at the end of the study and will be archived by the investigator.

When entering data, the system will immediately run consistency checks. Coherence controls will also be carried out using SAS software.

9 Statistics

9.1 Number of participants

We hypothesize that 60 % of patients will be improved in the treatment group against 15 % in the placebo group. It is therefore necessary to include 22 patients in each group to reach an 80% power with a 5% alpha (bilateral), leading to 44 patients overall (Fisher exact test).

Taking into account early withdrawal and patients who may be lost to follow-up, we are going to include 24 patients in each group, that is to say, a total of 48 patients.

9.2 Statistical analysis plan

The following section includes the main elements of the statistical analysis plan. This plan may be revised to take into account any amendments to the protocol and to make changes in order to adapt to the occurrence of unexpected events in the course of the study and which may have an impact on the analysis of the data.

These possible revisions will be carried out before the database is frozen.

At the end of the study, the data analysis will be carried out by the Clinical Research Unit at the Pole IMER (Department of [name], Hospices Civils de Lyon), who will have the randomization codes.

In case of scattered numbers of ointments across patients, the analyses would be repeated with an adjustment for the number of ointments or would be broken into subgroup analysis.

9.2.1 Analysis populations

9.2.1.1 “Efficacy” population in intention to treat

This population will be composed of all the randomized patients. If patients stop the study treatment, their follow-up will be maintained in order to obtain the epistaxis grids.

9.2.1.2 “Efficacy” population per protocol

This population will be composed of all the patients who have received all the treatments set out in the protocol. A treatment will be considered complete if the patient received at least a total of 60 administrations out of 84 (twice a day for 42 days) envisaged by the protocol.

9.2.1.3 “Safety” population

This population will be composed of all the patients who have received at least one ointment.

9.2.2 Statistical methods

9.2.2.1 Populations

All the populations in the study will be presented with their numbers.

9.2.2.2 Deviation from the protocol

Any deviation from the protocol that may have an impact on the results of the study will be listed.

9.2.2.3 Initial characteristics

All the initial characteristics of the patients will be summarized by means of descriptive statistics (number, average, standard deviation, median, minimum and maximum for the quantitative variables and numbers and percentages for the qualitative variables).

9.2.2.4 Analysis of the main judgement criterion

The percentage of patients experiencing improvement in their nosebleeds will be computed in each group. An improvement is defined as a 30% reduction in the total duration of nosebleeds over 6 weeks after treatment, compared with the duration of the nosebleeds in the 6 weeks before the treatment.

The percentage of the two groups will be compared using a Fisher exact test, and the analysis will be performed on the intention to treat population.

Patients who stopped the treatment but who have epistaxis grids will be analyzed using their data. Patients who withdraw from the study before completing the follow-up will be considered as failures.

A descriptive listing will present for each patient: the duration of nosebleeds before treatment, during treatment, after treatment, the treatment group, the number of consecutive days of treatment, the total number of days of treatment.

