1. Tolerance of tacrolimus nasal administration for 6 weeks, throughout the study.
2. Efficacy of the treatment on progress in the
 - clinical parameters:
 - Nosebleed duration
 - Number of nosebleeds
 - Number of transfusions of red blood cells
 - Quality of life
 - ESS = Epistaxis Severity Score
 - biological parameters: hemoglobin and serum ferritin concentrations

[figure not shown]
These parameters will be evaluated at the end of the 6 weeks of treatment (V2) and at the end of 6 weeks' follow-up (V3).
3. Systemic absorption after 1, 3 and 6 weeks of nasal administration.

Methodology

This is a phase II multicenter, randomized study carried out in double blind.

Number of patients: 48 patients will be randomized with an active/placebo ratio = 1:1.

For all patients, monitoring will be for 84 days (6 weeks' treatment + 6 weeks' follow-up).

For safety reasons, as no tolerance data are available with a nasal administration, we decided to include patients sequentially. We designed an inclusion scheme in 3 or 4 steps. An independent safety committee will give its recommendations on the continuation of the study.

Product tested:

The treatment tested is Tacrolimus, manufactured by the laboratories Astellas and marketed under the name of Protopic® (tacrolimus at 0.1%). For the study, the ointment will be used as is.

The comparative treatment, placebo, is the same formulation as the active product but without tacrolimus. One tube of product is delivered to patients, for administrations twice daily for 6 weeks.

Patients:

Inclusion criteria:

- Age \geq 18 years.
- Patients who have given their free informed and signed consent.
- Patients affiliated to a social security scheme or similar.
- Patients monitored for clinically confirmed HHT (presence of at least 3 Curaçao criteria) and/or confirmed by molecular biology.
- Patients presenting nosebleeds with total duration \geq 30 minutes for 6 weeks prior to the time of inclusion justified by completed follow-up grids.

Exclusion criteria:

- Women who are pregnant or nursing (lactating), women of child-bearing potential without reliable contraception.
- Patients not affiliated to a social security scheme.
- Patients who are protected adults under the terms of the law (French Public Health Code).
- Refusal to consent.
- Patients for whom the diagnosis of HHT has not been confirmed clinically and/or by molecular biology.

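### Efficiency gain, not an error: Boschloo's exact test would keep the 5% limit and is never less powerful than the planned Fisher test, adding 4.6 points of power at 60% vs 15% with exactly 24 per arm

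*Combined protocol and SAP*

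**What the plan says.** The primary endpoint is a responder proportion. Section 9.2.2.4 reads: "The percentage of the two groups will be compared using a Fisher exact test". The analysis set is intention to treat, which section 9.2.1.1 defines: "This population will be composed of all the randomized patients". Patients who withdraw are counted as failures (9.2.2.4, 9.2.2.6), so they stay in the denominator.

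The sample size in section 9.1 uses the same test. The assumption is: "We hypothesize that 60 % of patients will be improved in the treatment group against 15 % in the placebo group". The result is "22 patients in each group to reach an 80% power with a 5% alpha (bilateral), leading to 44 patients overall (Fisher exact test"). After an allowance for withdrawal, "we are going to include 24 patients in each group, that is to say, a total of 48 patients". The Synopsis gives the allocation: "48 patients will be randomized with an active/placebo ratio = 1:1".

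The plan mentions no unconditional exact test and gives no reason for preferring the conditional one. Section 4.4 describes a single pre-established randomisation list for all centres and states no block size. Section 9.2 allows the analysis plan to be revised until the database is frozen.

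**The concern.** Fisher's test conditions on the total number of responders. In small samples few tables share the same total, so its rejection probability under the null usually lies well below the nominal level. With equal arms of 24, a good part of the 5% error that section 9.1 allows goes unused.

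Boschloo's test takes the Fisher p-value as its ordering statistic and sets the cut-off so that the unconditional error rate, maximised over the unknown common response rate, is at most 5%. The Fisher rejection region already satisfies that limit, so Boschloo's region contains it. Its power is therefore at least as high at every pair of response rates.

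What is at stake is power in a 48-patient trial whose 60% and 15% rates carry no source in section 9.1. If the true difference is somewhat smaller, the test choice can decide whether power stays above 80%.

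**Working it through.** **Inputs.** Two-sided 5% level, 60% vs 15%, 22 per arm raised to 24 (9.1); 1:1 allocation (Synopsis); all randomised patients analysed (9.2.1.1). Other rate pairs and unequal splits are my assumptions, to show the range.

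**Method.** For arm sizes n₁ (active) and n₂ (placebo), list all (n₁+1)(n₂+1) tables. Let p_F(a,b) be the two-sided Fisher p-value with a and b responders.
- Fisher region: R_F = {(a,b): p_F ≤ 0.05}.
- Rejection probability: Pr(R; π₁, π₂) = Σ over R of Bin(a; n₁, π₁) × Bin(b; n₂, π₂).
- Size: the maximum over π of Pr(R; π, π), on a grid from 0.001 to 0.999.
- Boschloo region: R_B = {(a,b): p_F ≤ c}, with c the largest cut-off for which the size is at most 5%.

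**1. The plan's own figure.** Fisher power at 60% vs 15% is 79.9% with 21 per arm and 82.7% with 22. The stated 22 per group reproduces. With 24 per arm, power is 87.6%.

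**2. True size at 24 per arm.** Fisher: maximum 2.94% (at a common rate of 50%), 2.41% at a common rate of 15%, and 2.65% at 37.5%, the mean of the two design rates. Boschloo: c = 0.0798, maximum size 4.90%, 20 tables added and none lost.

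**3. Power at 24 per arm.**

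| Active vs placebo | Fisher | Boschloo | Gain (points) |
|---|---|---|---|
| 60% vs 15% | 87.6% | 92.2% | 4.6 |
| 55% vs 15% | 78.5% | 85.1% | 6.6 |
| 50% vs 15% | 66.8% | 74.7% | 7.9 |
| 45% vs 15% | 53.4% | 61.5% | 8.1 |
| 60% vs 20% | 76.0% | 83.0% | 7.0 |
| 60% vs 25% | 62.0% | 70.0% | 8.1 |
| 60% vs 30% | 47.1% | 54.7% | 7.7 |

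Withdrawals lower both rates because they count as failures. If two of 24 per arm withdraw (assumed), the rates become 60% × 22/24 = 55% and 15% × 22/24 = 13.75%. Power is then 82.0% with Fisher and 87.7% with Boschloo, a gain of 5.7 points.

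**4. One table by hand.** Take 11/24 vs 4/24 responders, 15 in total. The upper tail is Σ C(24,k)·C(24,15−k)/C(48,15) for k = 11 to 15, which is 0.02426 + 0.00501 + 0.00063 + 0.00004 + 0.000001 = 0.0299. Doubling, which is exact with equal arms, gives Fisher p = 0.060. The Boschloo p-value is the maximum over π of the probability that p_F is no larger than this, which is 0.032. The two tests reach opposite conclusions on this result.

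**5. Unequal splits.** The ranges cover both directions of imbalance.

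| Split | Fisher max. size | Cut-off c | Gain at 60/15 | Gain at 60/30 |
|---|---|---|---|---|
| 24/24 | 2.94% | 0.0798 | 4.6 | 7.7 |
| 24/23 | 4.01% | 0.0599 | 1.0–1.2 | 0.3–0.5 |
| 23/25 | 3.98% | 0.0677 | 1.4–2.3 | 0.5–1.1 |
| 22/26 | 4.23% | 0.0650 | 0.8–1.8 | 0.2–0.7 |

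At 50/15 and 45/15 the gain stays at about 3 to 7 points over these unequal splits. Boschloo's maximum size stays at or below 5% throughout, and it never rejects fewer tables than Fisher.

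**The case against.** The best case for leaving the plan alone has three parts.

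First, nothing is broken. Fisher's test controls the error, is pre-specified, agrees with the sizing method, and gives more than the promised 80% under the plan's own rates. All of this stands, so the point can only be an optional improvement.

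Second, much of the conservatism belongs to equal arms, and the documents do not guarantee equal arms. No block size is stated in section 4.4, and recruitment is stepped and may stop early (section 2.3). This also stands, and it limits the size of the gain. From the 24/24 table a reader might infer that the test choice costs most where the 15% placebo rate proves too low. That holds only with equal arms: at 60% vs 30% the gain falls from 7.7 points to about 1 or less once the split is off by one or two patients. Boschloo does not rescue the design there either, since 54.7% power at 24/24 is still inadequate.

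Third, some statisticians prefer conditional inference for a 2×2 table. That is a respectable position. However, section 9.1 states its requirements as a two-sided 5% limit and power. Both tests meet the limit, and one has at least the other's power everywhere.

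**Conclusion.** The point holds as a low-cost efficiency improvement. At exactly 24 per arm, Fisher's test uses at most 2.9% of the permitted 5%. Boschloo's test uses at most 4.9% and gains 4.6 points at the design rates, and 6.6 to 8.1 points at the other rate pairs tabulated for that split. Two plausible departures, 55% vs 15% and 60% vs 20%, take Fisher below 80% while Boschloo stays above it. With a one- or two-patient departure from 24/24, expect about 1 to 2 points at 60% vs 15%, about 1 or less at 60% vs 30%, and about 3 to 7 at 50% vs 15% and 45% vs 15%.

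Two stronger readings are not supported. A reader might infer that the trial is underpowered or the analysis invalid, but the documents' own figures reproduce and exceed the target. A reader might also infer that the sample could be cut, since Boschloo with 21 per arm (87.4%) nearly matches Fisher with 24 at 60% vs 15%. That rests on unsourced rates and on equal arms, so the margin is better kept.

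The figures assume independent binomial outcomes and recruitment to the planned 48, or within one patient of it.

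**What to change.** Before the database freeze and before any unblinded look at efficacy, amend section 9.2.2.4 as follows:
- Boschloo's exact test is the sole decisive primary test, two-sided at 5%.
- Tables are ordered by the two-sided Fisher p-value, and the size is maximised over the common response rate.
- The p-value is computed for the realised arm sizes. The cut-off of 0.0798 applies only to 24/24 and must not be written in as a constant.
- Fisher's p-value is reported as supportive, with no role in the conclusion. This settles in advance what happens when it falls between 0.05 and the Boschloo cut-off.

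Leave section 9.1 and the 48 patients unchanged. A sample size derived for Fisher's test is conservative for Boschloo's.

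The cost is a few sentences in the analysis plan and perhaps a few lines of non-default code. No patients, visits or data are added. The downside is that some readers prefer the conditional test; the supportive Fisher p-value gives them that result.

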4.4 Randomization, blinding and lifting the blind

The randomization process will be centralized. Allocation of a randomization arm to a patient included will be made by IWRS (Interactive Web Response System), on the basis of a unique randomization list for all investigation centers.

The lists of randomization will be pre-established, by the “Pole IMER” at the Hospices Civils de Lyon – Clinical Research Unit.

Clinsight (Ennov clinical) software will be used to manage this study.

During the inclusion visit, after verifying the inclusion criteria, the investigator connects to the platform to include the patients in the eCRF. This will assign an identification number. When inclusion is validated, the patient is randomized and a treatment code is allocated by the system. The treatment is then dispensed by the pharmacy at the Hospital Center.

This will be a double blind study in which neither the patient nor the investigator will be aware of the nature of the treatment administered so as to annul any bias in the follow-up and measurements.

Tubes of Tacrolimus 0.1% or placebo will be identical and will have appropriate labeling.

Should a serious adverse event occur, the main investigator, the co-investigators or the sponsor may request that the Anti-Poison Center in Lyon lift the blind 24h/24h (the phone number is written on the clinical trial participation card). The written detailed procedures for lifting the blind will be given to the investigators and the Anti-Poison Center in Lyon.

All requests for unblinding must be justified. Most often, study drug discontinuation and knowledge of the possible treatment assignments are enough to treat a study patient who presents with an emergency condition. When the investigator asks for unblinding, he/she must provide patient identifying information, the date, and the reason for unblinding. The investigator will be informed of the details of the drug treatment.

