6.2 Inclusion visit (V1)

Patients will be seen at a consultation for the treatment by a doctor and a clinical research assistant from the center if possible.

At this visit:

- The investigator will once again inform the patients about the study.
- The nosebleed grids completed by the patient in the 6 weeks prior to the treatment will be collected (Appendix 1: Nosebleed monitoring grid).
- The inclusion and exclusion criteria will be verified and the consent form will be signed. The investigator connects to the platform, includes the patient and an identification number will be assigned to the patient.
- The patient will undergo a clinical examination, including blood pressure and heart rate.
- A urinary pregnancy test will be performed for all female patients of child-bearing age. The investigator will inform these patients that there is no data available in pregnant women and they must use an effective contraceptive method (combined hormonal contraceptive, implant, intra-uterine device). The use of any other means, such as condom, will be left to the judgment of the investigator; the patient will have to give her commitment which will be recorded in the medical file.
- The number of red blood cell transfusions in the 6 weeks prior to administration of the treatment will be noted (as noted by the patient on the nosebleed grids).
- Any concomitant treatments will be noted.

If all the criteria are validated:

- The examination will be completed by a set of biological blood samples (2 x 5 mL tubes) for hemoglobinemia and serum ferritin.

- An ENT examination will be carried out (Appendix 3: Monitoring ENT examination).
- The ESS questionnaire is completed by patient (Appendix 2).
- An SF36 quality of life questionnaire will be given to the patient for completion.
- The nosebleed grids will be given to the patient for ENT monitoring during the 6 weeks of treatment (Appendix 1: Nosebleed monitoring grid). Specific boxes are provided to mark the two daily administrations, in order to verify observance of the treatment. If convenient for the patient a connexion code can be provided to allow them to complete these grids online on eCRF.

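### The primary responder test makes no use of baseline nosebleed duration; a prespecified baseline-adjusted re-randomisation test would be a modest, nearly free gain in efficiency, not the repair of an error

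*Combined protocol and SAP*

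**What the plan says.** All references are to the combined protocol and SAP.

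- **Endpoint and test (9.2.2.4).** "An improvement is defined as a 30% reduction in the total duration of nosebleeds over 6 weeks after treatment", relative to the 6 weeks before treatment. Then: "The percentage of the two groups will be compared using a Fisher exact test", on all randomised patients. Patients who withdraw before completing follow-up count as failures.
- **Sample size (9.1).** "We hypothesize that 60 % of patients will be improved in the treatment group against 15 % in the placebo group". The 22 per group is sized "to reach an 80% power with a 5% alpha (bilateral), leading to 44 patients overall (Fisher exact test"). Then "we are going to include 24 patients in each group, that is to say, a total of 48 patients".
- **Baseline (6.2).** "The nosebleed grids completed by the patient in the 6 weeks prior to the treatment will be collected". Section 4.2.5 excludes anyone with more than 7 missing days on that grid, so a usable baseline exists for every patient.
- **Allocation (4.4).** Assignment is made "on the basis of a unique randomization list for all investigation centers". No stratification factor is named.
- **Adjustment elsewhere.** Section 9.2 allows an adjustment for the number of ointment applications. Mixed models appear only for the secondary criteria (9.2.2.5). No baseline-adjusted analysis of the responder endpoint is planned.

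**The concern.** Dividing by baseline in the responder definition is not the same as adjusting for baseline. A change score stays correlated with its own starting value through regression to the mean, and patients enter on a minimum amount of bleeding in that same window. For two equally variable log durations with correlation rho, the correlation of change with baseline is -sqrt((1 - rho)/2).

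Nothing stated balances baseline between arms. With 24 per arm, the difference in mean log baseline has a standard error of sqrt(2/24) = 0.29 SD, so a gap above 0.3 SD arises by chance in about 30% of trials. If baseline predicts response, such a gap adds noise to the responder difference, and the unadjusted test leaves the information unused. At stake is the chance of missing a real effect in a 48-patient trial in a rare disease, where more patients are hard to find but this variable is already in hand.

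**Working it through.** **1. The plan's own figure.** Inputs from 9.1: 60% v 15%, two-sided 5%, Fisher's exact test. Summing over both binomial distributions, power is 79.9% at 21 per arm, 82.7% at 22 and 87.6% at 24. The stated 22 per group reproduces.

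With two of 24 per arm scored as failures, the rates become 60% x 22/24 = 55% and 15% x 22/24 = 13.75%. Fisher power is then 82.0%.

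**2. What Fisher's discreteness costs.** At 24 per arm the true size of the nominal 5% Fisher test is at most 2.9%. Boschloo's exact test, which uses no covariate and holds the 5% level, has 92.2% power at 60% v 15%. The gain is 92.2 - 87.6 = 4.6 points without using baseline.

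**3. Adding baseline.** The documents give no SD and no before/after correlation, so both are assumed. Model: log baseline normal, truncated at 30 minutes, median 150 minutes, SD 1.0; post-treatment log duration with correlation rho; shifts calibrated to 60% and 15% responders; 3,000 trials. The adjusted test permutes residuals from a logistic model of response on log baseline (999 permutations). Power in %:

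| rho | Fisher | Boschloo | Adjusted | Adjusted minus Fisher | Adjusted minus Boschloo |
|---|---|---|---|---|---|
| 0.3 | 87.1 | 91.3 | 96.0 | 8.9 | 4.7 |
| 0.5 | 88.1 | 92.8 | 94.7 | 6.6 | 1.9 |
| 0.7 | 88.3 | 92.7 | 93.8 | 5.5 | 1.1 |
| 0.85 | 88.2 | 93.1 | 93.1 | 4.9 | 0.0 |

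A second simulation gave 95.5, 95.8, 93.4 and 93.7 for the adjusted test at the same four values. Against the exact 92.2 for Boschloo, that is +3.3, +3.6, +1.2 and +1.5. Rejection under the null was 4.2-5.7% in the first and 4.5-5.0% in the second.

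With two withdrawals per arm scored as failures, Fisher / Boschloo / adjusted were 82.1 / 88.9 / 93.3 (rho 0.3), 82.7 / 88.3 / 91.8 (0.5) and 83.0 / 88.3 / 90.4 (0.7). Adjustment alone then adds 4.4, 3.5 and 2.1 points.

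**4. A different model.** Here response comes from a latent normal variable with assumed correlation r to baseline (8,000 trials, simulation error about 0.3-0.4 points). Gain over Fisher for r = 0, 0.2, 0.3, 0.4, 0.5, 0.6:

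- residual re-randomisation test: +3.9, +4.3, +5.1, +6.9, +7.7, +9.3;
- the same test against mid-p Fisher without a covariate: -0.9, 0.0, +0.9, +2.3, +2.9, +4.8;
- exact test stratified at the baseline median: +0.9, +0.9, +1.6, +2.9, +4.2, +5.0.

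The +3.9 at r = 0, where baseline carries no information, confirms that this part of the gain comes from removing discreteness.

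**5. Which rho fits the plan's 15% placebo rate?** If the placebo median does not drift, 15% of patients falling by at least 30% requires an SD of log change of |ln 0.7| / 1.036 = 0.344. With equal variances, rho = 1 - 0.344²/(2 x SD²). At SD 1.0 this is 1 - 0.118/2 = 0.94, and the correlation of change with baseline is -sqrt(0.059/2) = -0.17. Over SD 0.6-1.3 that correlation is 0.13-0.29 in size.

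Conversely, in the model of step 3 (SD 1.0), rho = 0.3, 0.5 and 0.7 reach 15% only if the typical placebo patient's bleeding rises by a factor of 2.32, 1.94 and 1.54.

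Under near-stable placebo bleeding, adjusted v Boschloo power is 92.4 v 92.8 (SD 1.0, rho 0.94), 93.0 v 92.3 (SD 0.7, rho 0.85) and 93.1 v 93.5 (SD 0.7, rho 0.9), from 2,500 trials each. Those differences are within simulation error.

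**The case against.** The strongest reply is that nothing here needs repair. Fisher's test is valid, prespecified and the one used for the sample size, and the trial exceeds its own power target. A chance baseline imbalance does not invalidate a randomised comparison. Baseline characteristics are summarised, nosebleed durations are listed per patient, and mixed models compare duration over the three periods, though only as secondary analyses. All of that stands.

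A reader might also infer more than the documents support:

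- *That baseline adjustment by itself buys 5 to 9 points.* It does not. Most of the gain over Fisher is available from an unadjusted exact test, and the larger totals need a low rho at which placebo bleeding would rise 1.5 to 2.3 fold. Nothing in the documents suggests such worsening.
- *That baseline is a strong predictor of response.* No association is reported. Even at an assumed rho of 0.5, where log change correlates -0.5 with baseline, the correlation with the binary placebo response is only 0.32-0.33.
- *That patients near the 30-minute entry threshold have little room to respond.* The criterion is proportional: 30 x 0.7 = 21 minutes is enough.
- *That the adjusted test is the same exact procedure with a covariate added.* It is a different procedure. The closest exact analogue, stratified at the baseline median, gains only about 1 to 5 points.

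What remains is that the proposed test outperformed the planned one in every setting tried, at almost no cost.

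**Conclusion.** The concern holds as an efficiency improvement, not as an error. At 60% v 15% with 24 per arm, the adjusted re-randomisation test gains about 3 to 9 points over Fisher's 87.6%, with type I error near 5%. About 4 to 5 points of that come from removing Fisher's conservatism.

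Baseline adjustment itself contributes about 0 to 5 points: about 3 to 5 at an assumed rho of 0.3 to 0.5 (one run gave 1.9 at 0.5), 1 to 2 at 0.7, and about none if the placebo median is stable at the planned 15% rate. The split rests on assumed values of rho and SD; the exact Fisher and Boschloo figures rest only on the plan's inputs. The plan is not underpowered on its own assumptions, and its primary test is not invalid.

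**What to change.** In 9.2.2.4, before the database is frozen (9.2 permits revision until then):

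- Make the primary test a two-sided re-randomisation test of the arm difference in responders, adjusted for log baseline 6-week duration: residuals from a logistic model of response on log baseline, with allocation permuted as the list was generated. State the number of permutations and fix the random seed. Section 4.4 does not describe any blocking, so the list's restrictions need to be written down for this purpose.
- Leave the responder definition, the intention-to-treat set and the failure rules unchanged.
- Report the baseline-standardised risk difference with its 95% CI.
- Keep Fisher's test as the unadjusted sensitivity analysis, and state that the adjusted test carries the primary conclusion.

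The cost is SAP wording and a short program. No extra patient, visit or data item is needed. The downside is a test that is less familiar than Fisher's and depends on a fixed seed. It must be settled before unblinding, because an adjustment chosen afterwards would not be credible.
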